5.8.2 Withdrawal from the Trial

Subjects may withdraw from the trial at any time for any reason. If a subject withdraws from the trial, they will no longer receive treatment or be followed at scheduled protocol visits.

A subject must be withdrawn from the trial if:

- The subject or legal representative (such as parent or legal representative) withdraws consent from the trial.
- The subject is lost to follow-up

Specific details regarding procedures to be performed at the time of withdrawal from the trial including specific details regarding withdrawal from Future Biomedical Research are outlined in Section 7.1.4 – Other Procedures.

5.9 Subject Replacement Strategy

In Parts 1, 2, 4, and 5, additional subjects may be enrolled in a given cohort to ensure that the required number of evaluable subjects in each cohort is achieved. A subject who discontinues the trial for progressive disease or a drug-related AE will not be replaced and will be counted in the evaluable population of subjects for the respective cohort. Further details are provided in Section 8.2.4.2.

5.9.1 Parts 1, 2, 4, and 5: Subject Replacement Strategy - Dose Limiting Toxicity

Any subject who does not complete the 6-week DLT evaluation period in Parts 1, 2, 4, or 5 (i.e., Cycle 1, initiated with the first pembrolizumab dose) and does not experience any DLT will be replaced, except those who discontinue due to non-DLT toxicity that is nevertheless drug-related (or suspected to be drug-related). In addition, any subject who misses $\geq 50\%$ of PK or PD samples or misses 3 consecutive doses of study medication immediately prior to PK blood sampling may be replaced at the discretion of the Sponsor. In Parts 4 and 5, any subject who discontinues trametinib during the trametinib monotherapy run-in period is not considered evaluable for DLTs for the MK+T combination, even if the subject discontinued due to a DLT, and will be replaced.

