5.2.4.3 Dose Limiting Toxicity

Toxicities will be graded using National Cancer Institute (NCI) CTCAE Version 4.0. A DLT evaluable subject is defined as a subject who receives treatment for the 6-week dose-limiting toxicity (DLT) observation period and who receives at least 66% of all planned treatments. A subject who does not receive at least 66% of planned treatment due to AEs that are unrelated to study treatment will not be considered evaluable for DLTs and may be replaced as needed during dose escalation or dose confirmation. More than 3 or 6 subjects may be enrolled to a given dose level if needed to replace subjects who are not evaluable for DLT or to ensure a thorough evaluation of a given dose level during the dose escalation part of the study. An event will be considered a dose-limiting toxicity (DLT) if it occurs during the first cycle of treatment in dose identification and confirmation subjects (first 6 weeks after initiating pembrolizumab treatment) and meets at least one of the following criteria:

- Clinically significant hematologic toxicity (e.g. grade 4 neutropenia lasting more than 7 days or accompanied by neutropenic fever, or Grade 4 thrombocytopenia of any duration)
- Clinically significant Grade ≥ 3 non-hematologic toxicity that has not been previously identified for either pembrolizumab or dabrafenib/trametinib and cannot be controlled with routine supportive measures (e.g. anti-emetics)
- Clinically significant Grade ≥ 3 non-hematologic toxicities that are known to occur with either pembrolizumab or dabrafenib/trametinib but that cannot be controlled using the recommended product-specific supportive measures (e.g. steroids for pembrolizumab-related immune toxicities)
- Drug-related toxicity, regardless of CTCAE grade, that results in an interruption of any component of study therapy during Cycle 1 for more than 21 consecutive days and cannot be controlled within 2 weeks from its onset
- Any other Grade 2 or greater non-hematological toxicity that in the judgment of the investigator and Sponsor is dose limiting, with the exception of mild or moderate immune-mediated adverse reactions or symptomatic endocrinopathy attributable to pembrolizumab
- Liver chemistries meeting stopping guidelines (as outlined in Section 5.6.1.1.15):
 1. ALT or AST ≥ 3 xULN and bilirubin ≥ 2 xULN (>35% direct bilirubin) (or ALT/AST ≥ 3 xULN and INR >1.5, if INR measured)

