8.2.4.2 Safety Analysis Populations

The ASaT population will be used for the analysis of safety data in this study. In all parts of the study, the ASaT population consists of all subjects who received at least one dose of study treatment. In Parts 4 and 5, subjects treated during the trametinib run-in period will be included in the ASaT population even if they discontinued treatment before receiving pembrolizumab. In case of treatment administration errors, subjects will be analyzed according to the treatment they actually received.

At least one laboratory or vital sign measurement obtained subsequent to at least one dose of study treatment is required for inclusion in the analysis of each specific parameter. To assess change from baseline, a baseline measurement is also required.

The DLT analysis will be performed on a DLT-evaluable population.

In Parts 1 and 2, a DLT evaluable subject is defined as a subject who receives at least 66% of all planned treatments during the 6-week DLT observation period (i.e., Cycle 1, initiated with

the first pembrolizumab dose) or a subject who discontinues the DLT observation period due to a DLT. In Parts 4 and 5, a DLT evaluable subject is defined as a subject who receives at least 66% of all planned treatments during the 6-week DLT observation period (i.e., following the trametinib run-in period in Cycle 1, initiated with the first pembrolizumab dose) or a subject who discontinues the DLT observation period due to a DLT. In Parts 4 and 5, any subject who discontinues trametinib during the trametinib monotherapy run-in period is not considered evaluable for DLTs for the (MK+T) combination, even if the subject discontinued due to a DLT.

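### Sections 5.2.4.3, 5.9, 5.9.1 and 8.2.4.2 give conflicting DLT-evaluability rules, and on their literal text some DLT subjects fall outside the population that is counted

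*Combined protocol and SAP*

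**What the plan says.** - **Section 5.2.4.3** sets two conditions that must both hold. The first concerns the window: "A DLT evaluable subject is defined as a subject who receives treatment for the 6-week dose-limiting toxicity (DLT) observation period". The second concerns exposure, and limits the definition to a subject "who receives at least 66% of all planned treatments". It makes no exception for a subject whom a DLT stops. The next sentence addresses only one cause of low exposure, and takes such a subject out of the evaluable set: "A subject who does not receive at least 66% of planned treatment due to AEs that are unrelated to study treatment will not be considered".
- **Section 8.2.4.2** runs the DLT analysis on the DLT-evaluable population. That is a subject with at least 66% of planned treatments in the 6-week window, or "a subject who discontinues the DLT observation period due to a DLT".
- **Section 5.9** says "A subject who discontinues the trial for progressive disease or a drug-related AE will not be replaced and will be counted in the evaluable population", and refers to 8.2.4.2 for detail.
- **Section 5.9.1** says that a subject who does not complete the window "and does not experience any DLT will be replaced, except those who discontinue due to non-DLT toxicity that is nevertheless drug-related"; suspicion of a drug relation is enough for that exception. Progressive disease is not in it. It also says that a subject who "misses 3 consecutive doses of study medication immediately prior to PK blood sampling may be replaced at the discretion of the Sponsor".
- **DLT criteria (5.2.4.3)** include a drug-related toxicity "that results in an interruption of any component of study therapy during Cycle 1 for more than 21 consecutive days" that cannot be controlled within 2 weeks of onset.
- **Section 5.2.4.1.2** lets a subject with a DLT remain on study under stated conditions.
- **Sections 5.2.4.2.1 and 5.2.4.2.2** base dose decisions on the number evaluable against the number who developed a DLT.

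**The concern.** DLT is the primary safety endpoint of Parts 1, 2, 4 and 5 (8.2.3.2), and the 3+3, TPI and mTPI rules work on very small counts. If the sections disagree on who is in the denominator, two teams with the same data can reach different dose decisions. If a DLT subject is left out, or a subject who was barely observed is counted as DLT-free, the decision moves toward accepting the dose. Section 8.2 says that no separate SAP will be issued, so no other analysis plan settles the matter.

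**Working it through.** **Step 1. The rules side by side**

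| Subject | 5.2.4.3 | 5.9 | 5.9.1 | 8.2.4.2 |
|---|---|---|---|---|
| (a) Leaves the window for PD, no DLT | Not evaluable (window not completed) | Counted, not replaced | Replaced | Evaluable only if ≥66% |
| (b) Stopped early by a DLT | Not evaluable on the literal text | Counted if drug-related | Not replaced under the main rule | Evaluable |
| (c) DLT, stays on study, <66% | Not evaluable | Silent | Not addressed | Not evaluable |
| (d) Drug-related non-DLT drop-out, <66% | Not evaluable on the literal text | Counted, not replaced | Not replaced | Not evaluable |

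**Step 2. Does case (c) arise?** Take an interruption lying within the 42-day Cycle 1 window. More than 21 days means at least 22, so at most 42 − 22 = 20 daily doses remain.
- Continuous MK+T, trametinib alone: 20/42 = 47.6%.
- Continuous MK+T, pooled with two pembrolizumab infusions: (20 + 2)/(42 + 2) = 22/44 = 50%.
- Triplet, pooled: planned 42 + 84 + 2 = 128. Trametinib alone held: 106/128 = 82.8%. Dabrafenib alone held: 84/128 = 65.6%. Both held: 62/128 = 48.4%.

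On continuous MK+T both readings fall below 66%. For the triplet the answer depends on the 66% denominator, which no section defines. Intermittent regimens also have planned off-days, so their percentages differ.

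**Step 3. Reproduce Table 13.** The plan gives a Beta(1,1) prior, target 0.30 and margins of 0.05. For x DLTs in n subjects the posterior is Beta(1+x, 1+n−x). The decision is the interval with the largest probability per unit length: E on (0, 0.25), S on (0.25, 0.35), D on (0.35, 1). DU applies if P(rate > 0.30) exceeds 0.95; that cut-off is an assumption, since it is not stated. All 93 cells in rows 0 to 8 match. For example:
- 4/8: E 0.20, S 1.23, D 1.27, so D.
- 4/9: E 0.31, S 1.70, D 1.16, so S.

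**Step 4. Effect of one subject**
- Counting one early-PD subject (5.9) rather than leaving that subject out: with 4 DLTs, n = 9 instead of 8. Table 13 moves from D to S, and Table 11 from DU to D.
- Leaving out one DLT subject, (x, n) to (x−1, n−1): Table 13 moves from D at 7/14 to S at 6/13, and from D at 5/10 to S at 4/9. Of the cells checked, 21 of 71 in Table 13 and 20 of 67 in Table 11 become less restrictive.
- In the 3+3, 2/3 (de-escalate) becomes 1/3 after a DLT-free replacement (expand).
- Case (d) goes the other way. Leaving out a DLT-free subject shrinks the denominator, for example from 4/9 (S) to 4/8 (D).

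**Step 5. Illustration of size.** The documents give no share of DLT subjects lost, so f = 25% is an assumption. If a share f is dropped and replaced, the counted rate is p(1−f)/(1−pf). At p = 0.40 this is 0.30/0.90 = 0.333. The 3+3 accepts with probability (1−p)³ + 3p(1−p)²[(1−p)³ + 3p(1−p)²]:
- p = 0.40: 0.216 + 0.432 × 0.648 = 0.496.
- p = 0.333: 0.296 + 0.444 × 0.741 = 0.626.

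With f = 50% the counted rate is 0.25 and acceptance is 0.778.

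**The case against.** The best defence is that the intent is clear. Section 8.2.4.2 keeps subjects who discontinue for a DLT. The main rule of 5.9.1 replaces only subjects without one. The Part 2 and Part 5 rules count subjects who developed a DLT. The low-exposure sentence in 5.2.4.3 names only unrelated AEs. DLTs are also listed (8.2.5.4) and, for the triplet, tabulated on all treated subjects (8.1.1), so none would vanish unseen. This is fair and limits the severity. It does not settle the PD conflict, where 5.9 and 5.9.1 give opposite instructions, and it does not bring case (c) into the written population. Scheduled imaging starts at Week 13, 15 or 17, after the DLT window, so early PD would come from unscheduled or clinical assessment. Case (a) is therefore real but probably uncommon.

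A reader might infer more than the documents support:
- **That every interruption DLT is non-evaluable by construction.** This fails for the triplet on a pooled denominator (82.8% with trametinib alone held).
- **That all the conflicts favour a more toxic dose.** Case (d) does not.
- **That PK-based replacement erases a DLT.** No passage removes the replaced subject's DLT from the count; the text is only silent.
- **That the run-in exclusion is part of the conflict.** Sections 5.9.1 and 8.2.4.2 agree on it, so it is a deliberate rule.

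**Conclusion.** The four sections conflict in current operative text and must be reconciled. Cases (a), (b) and (d) are direct disagreements between sections. Case (c) is a gap that leaves a DLT subject outside both definitions, and on continuous MK+T the interruption criterion produces it. Losing a DLT subject, or counting an unobserved PD subject, shifts decisions toward accepting a dose; case (d) shifts them the other way. That one subject can change a table decision follows from the plan's own tables. The rise from 50% to 63% rests on the assumed 25% share and on a literal reading of the definitions, so it shows scale and is not an estimate. A reader might also conclude that the Part 3 triplet dose was chosen on a wrong count. Nothing in the documents shows that a DLT was actually dropped, and 5.2.5 reports the Part 3 final analysis as done. What remains live is the Part 4/5 dose decisions and the reported DLT analysis.

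**What to change.** Put one counting definition in 5.2.4.3, 5.9, 5.9.1 and 8.2.4.2. A subject is evaluable if any of these holds:
1. A DLT occurred in the 6-week combination window, whatever doses were received and whether or not treatment was discontinued.
2. There was no DLT, and the window was completed with at least 66% of planned treatments. State whether the 66% is per drug or pooled, and how planned off-days count.
3. The subject dropped out for drug-related toxicity that was not a DLT. Sections 5.9 and 5.9.1 already agree not to replace this subject, and 5.9 counts the subject; add that rule to 8.2.4.2.

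Subjects who leave early for PD without a DLT are non-evaluable and replaced, as in 5.9.1; remove progressive disease from the 5.9 sentence. Add a clause that a subject replaced for PK reasons still has any DLT counted. Leave the run-in exclusion unchanged.

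This alters counting only, not treatment. The cost is wording in four sections and possibly one or two extra replacement subjects per dose level.

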5.10 Beginning and End of the Trial

The overall trial begins when the first subject signs the informed consent form. The overall trial ends when the last subject completes the last trial visit, discontinues from the trial or is lost to follow-up (i.e. the subject is unable to be contacted by the investigator).

5.11 Clinical Criteria for Early Trial Termination

Early trial termination will be the result of the criteria specified below:

1. Quality or quantity of data recording is inaccurate or incomplete.
2. Poor adherence to protocol and regulatory requirements.
3. Incidence or severity of adverse drug reaction in this or other studies indicates a potential health hazard to subjects
4. Plans to modify or discontinue the development of the study drug(s).

Statistical criteria for stopping the trial are provided in Section 8.0 – Statistical Analysis Plan.

Enrollment will not be halted during the planned interim analysis.

In the event of Sponsor decision to no longer supply study drug, ample notification will be provided so that appropriate adjustments to subject treatment can be made.

Further recruitment in the trial or at (a) particular trial site(s) may be stopped due to insufficient compliance with the protocol, GCP and/or other applicable regulatory requirements, procedure-related problems or the number of discontinuations for administrative reasons is too high.

6.0 TRIAL FLOW CHART

6.1 Treatment Phase

6.1.1 Parts 1 and 2: Pembrolizumab Q3W Dosing with Trametinib and/or Dabrafenib

Trial Period:	Screening ⁹	Treatment (6-Week Cycle)										End of Treatment
Visit Number:	1	2	3	4	5	6	7	8	9	≥ 10	Discontinuation ²³	
Days	(-28 to -1)	1	8	15	22	29	36	1	22	1,22		
Cycle		1						2		≥ 3		
Scheduling Window (Days)		±3	±3	±3	±3	±3	±3	±3	±3	±3		
Administrative Procedures												
Informed Consent ¹	X											
Informed Consent for Future Biomedical Research (optional)	X											
Inclusion/Exclusion Criteria	X											
Subject Identification Card	X											
Demographics and Medical History ²	X											
Prior and Concomitant Medication Review ³	X	X	X	X	X	X	X	X	X	X	X	
Treatment Assignment		X										
Survival status ²⁸		←----->										
Clinical Procedures / Assessments												
Full Physical Examination ²⁷	X	X						X		X ²⁴		
Directed Physical Examination			X	X	X	X	X	X	X	X ²⁴	X	
Vital Signs and Weight ⁴	X	X	X	X	X	X	X	X	X	X	X	
12-Lead Electrocardiogram (ECG) ⁵	X	X						X		X ²⁵		
ECHO	X					X				X ²⁵		
Review Adverse Events ^{6,7,8}		X	X	X	X	X	X	X	X	X	X	
ECOG Performance Status	X	X						X		X ²⁵	X	

Trial Period:	Screening ⁹	Treatment (6-Week Cycle)									End of Treatment
Visit Number:	1	2	3	4	5	6	7	8	9	≥ 10	Discontinuation ²³
Days	(-28 to -1)	1	8	15	22	29	36	1	22	1,22	
Cycle		1						2		≥ 3	
Scheduling Window (Days)		±3	±3	±3	±3	±3	±3	±3	±3	±3	
Laboratory Procedures / Assessments⁹											
Pregnancy Test - Urine or Serum β-HCG ¹⁰	X										
CBC with Differential ¹¹	X	X	X	X	X	X	X	X	X	X ²⁵	X
Comprehensive Chemistry Panel ¹¹	X	X	X	X	X	X	X	X	X	X ²⁵	X
Urinalysis ¹¹	X	X	X	X	X	X	X	X	X	X ²⁵	X
PT/INR and aPTT ¹²	X	As clinically indicated									
Calculated Creatinine Clearance	X										
T3, FT4 and TSH ^{11,13}	X	X						X		X ¹³	X
Hepatitis B and C ¹⁴	X										
Blood for Future Biomedical Research ¹⁵ (optional)		X									
Drug Dispensation, Administration, and Associated Analyses											
pembrolizumab Administration (30-minute infusion)		X			X			X	X	X	
Pharmacokinetics of pembrolizumab ¹⁶		X			X			X		X ²⁵	
Anti-pembrolizumab Antibodies ¹⁷		X						X		X ²⁵	
Dispensation of Drug Kit		X			X			X	X	X ²⁵	
Pharmacokinetics of Dabrafenib and/or Trametinib ¹⁸					X			X		X ²⁵	X
Efficacy Measurements											
Tumor Imaging ¹⁹	X									X ²⁵	X
Tissue Collection and Pharmacodynamic Assessment											
BRAF Testing ²⁰	X										
Tumor Tissue Collection ²¹	X		X ²¹								X ²⁶
Correlative Blood Sample ²¹	X	X						X			X
Blood for Genetics ²²		X									
1 Written consent must be obtained prior to performing any protocol-specific procedure. Results of a test performed prior to the subject signing consent as part of routine clinical management are acceptable in lieu of a screening test if performed within the specified time frame (e.g. within 28 days prior to Day 1). Assign Baseline number when the study informed consent is signed. 2 Includes history of treatment for the primary diagnosis, including prior systemic, radiation treatment and surgical treatment, and best response to prior systemic treatments. Date of last prior cancer treatment must be documented. Radiographic studies performed prior to study entry may be collected for review by the investigator. 3 Prior Medications - Report all medications taken within 30 days of Visit 1 and all treatments for a prior cancer even if taken greater than 30 days prior to Visit 1. Concomitant Medications - Enter new medications started during the trial through the Safety Follow-Up visit. After the Safety Follow-Up visit, record all medications taken for SAEs and ECIs as defined in Section 7.2. 4 Vital signs to include temperature, pulse, respiratory rate and blood pressure. If a patient's baseline weight does not fluctuate by more than 10%, this weight can be used to calculate dose. Height will be measured at Visit 1 only. 5 Electrocardiogram (12-lead ECG) should be performed at Screening and post-infusion at visits indicated in the flow chart. 6 Adverse experiences and laboratory safety measurements will be graded per NCI CTCAE version 4.0. All adverse experiences, whether gradable by CTCAE or not, will also be evaluated for seriousness. 7 Any adverse experience of unknown etiology associated with trial treatment exposure should be evaluated to determine if it is possibly an Event of Clinical Interest (ECI).											

- 8 Evaluate patients for symptoms or clinical signs of non-cutaneous, new primary/recurrent malignancies before initiation of treatment, periodically during treatment, or as clinically indicated. Following discontinuation of dabrafenib, monitoring for non-cutaneous secondary/recurrent malignancies should continue for up to 6 months or until initiation of another anti-neoplastic therapy. Abnormal findings should be managed according to clinical practices.
- 9 Routine laboratory tests (chemistry; hematology) for screening should be performed within 10 days prior to the first dose of trial treatment. See Section 7.1.3 for details regarding laboratory tests.
- 10 For women of reproductive potential, a urine pregnancy test will be performed within 72 hours prior to first dose of trial treatment. If urine pregnancy results cannot be confirmed as negative, a serum pregnancy test, performed by the local study site laboratory, will be required. Pregnancy tests (serum and/or urine tests) should be repeated if required by local guidelines.
- 11 After Cycle 1, lab samples can be collected up to 48 hours prior to the scheduled time point. Laboratory results must be known and acceptable prior to dosing. See Section 7.1.3 for details regarding laboratory tests.
- 12 Coagulation factors (PT/INR and aPTT) should be monitored closely throughout the trial for any subject receiving anticoagulant therapy.
- 13 Thyroid function tests will be performed by a central laboratory only if the local laboratory is unable to perform this service. Following Cycle 4, testing will be performed every other cycle. In countries where T3 results are not available, FT3 results may be reported. See Section 7.1.3 for details regarding laboratory tests.
- 14 Testing will be performed by the local laboratory at Screening. Hepatitis B and Hepatitis C serologies should be obtained for subjects without a known history of Hepatitis B or C. Those with a known history are ineligible. Include HCV RNA (qualitative) and HBsAg.
- 15 Informed consent for Future Biomedical Research (FBR) samples must be obtained before the DNA sample is drawn. DNA sample for analysis should be obtained predose, on Day 1 (or with the next scheduled blood draw), as the last sample drawn, on allocated subjects only, or at a later date as soon as the informed consent is obtained. This sample should only be taken once from each subject. See Section 12.2 for guidance regarding the collection and management of specimens for FBR.
- 16 Pre-dose and post-dose serum samples for PK of pembrolizumab will be collected on Day 1 and Day 22 of Cycle 1 and Day 1 of Cycle 2. Thereafter, only pre-dose (C_{trough}) PK serum samples will be collected at Day 1 of every alternate cycle (i.e., Day 1 of Cycle 3, Day 1 of Cycle 5, etc.). All pre-dose (C_{trough}) samples should be collected within 24 hours before the start of infusion of pembrolizumab and, if blood is collected for anti-pembrolizumab antibodies, at the same time blood sample for anti-pembrolizumab antibodies is collected. All post-dose PK samples should be collected within 30 minutes after the end of infusion of pembrolizumab. One additional post-dose sample should be collected between 24 and 96 hours following C1D1. Procedures for collection of samples are described in the Procedures Manual.
- 17 Blood for anti-pembrolizumab antibodies should be collected on Day 1 of Cycles 1, 2, 3 and every other cycle thereafter (Cycle 5, Cycle 7, etc.). During pembrolizumab treatment, all samples should be drawn within 24 hours before infusion of pembrolizumab at the same time as blood collection for pre-dose (C_{trough}) PK serum samples of pembrolizumab.
- 18 On C1D22, both pre-dose and post-dose plasma samples for PK of trametinib and dabrafenib will be collected. On C1D22, morning dose(s) should be withheld until after PK (pre-dose) sample has been drawn. On C1D22, post-dose PK samples for trametinib and/or dabrafenib should be drawn (1) at the same time as when the post-dose pembrolizumab PK sample is drawn (the end of infusion), and, (2) at approximately 4-6 hours post-dose. On C2D1, subjects should take their morning dose at home. A post-dose sample will be obtained during study visit. Thereafter, PK plasma samples will be collected at Day 1 of every alternate cycle (i.e., Day 1 of Cycle 3, Day 1 of Cycle 5, etc.) during study visit. If visit is in the morning, subjects will be asked to withhold their morning dose; if visit is in the afternoon, subjects will be asked to take their morning dose as usual. Procedures for collection of samples are described in the Procedures Manual.
- 19 The initial tumor imaging will be performed within 28 days prior to the date of allocation. Scans performed as part of routine clinical management are acceptable for use as the screening scan if they are of diagnostic quality and performed within 28 days prior to the first dose of trial treatment. CT scans are the required modality for measurable disease unless a subject has a clinical condition, e.g., severe contrast allergy. The same imaging technique has to be used for the subject throughout the study. The visit window for subsequent imaging is +/- 7 days. If there is progressive disease, radiologic assessment/tumor imaging should be obtained at least four weeks from scan date for confirmation. CT timing should follow calendar days and should not be adjusted for delays in cycle starts. The process for collection of CT images is described in the Procedures Manual. Tumor imaging will be performed every 6 weeks (or whenever clinically indicated) starting at Week 13 while the subject remains on study therapy; after 18 months, tumor imaging will be performed every 12 weeks (or whenever clinically indicated) while the subject remains on study therapy. Per the modified RECIST 1.1 used in this protocol, if imaging shows progressive disease, the imaging assessment should be repeated at a minimum of 4 weeks later in order to confirm progressive disease as described in Section 4.2.3.1.
- 20 BRAF V600E or K mutation analysis should be performed by sites during screening in subjects without documented BRAF status. This specimen may be collected any time from the initial diagnosis to the study entry and may be an archival tissue sample (within 6 months of study entry). BRAF analysis may be performed at a local laboratory, provided that the methodology is able to detect V600E and/or V600K mutations. A sample from the originally-tested tissue block must be collected and stored at the central laboratory for possible assay at a later date (i.e., in the event that BRAF status must be confirmed). Detailed instructions for tissue collection, processing and shipment are provided in the Procedures Manual.

21 In order to be eligible for the study, all subjects must provide a tumor tissue specimen for biomarker analysis and blood samples for pharmacodynamic assessment. The tissue specimen may be collected any time from the initial diagnosis to the study entry and may be an archival tissue sample (within 90 days of Study Day 1=first dose(s) of study treatment) if it is not feasible to obtain a fresh biopsy not previously irradiated. Site documentation that the sample has been shipped to the biomarker analysis laboratory is sufficient evidence to meet eligibility criterion. If a tumor biopsy was obtained of a target lesion during eligibility assessment, it is preferred to obtain a new baseline scan. Biopsy of lesions on study should be limited to non-target lesions or new lesions if their pathologic etiology is ambiguous. The tissue sample should have proper size to enable multiple planned biomarker analyses, but not artificially decrease the longest diameter of the lesion. Additionally, a fresh biopsy should be obtained 10-14 days following initiation of study treatment for Parts 1 and 2 of the study. The fresh biopsy at 10-14 days following initiation of study treatment is optional in Part 3 of the study. Detailed instructions for blood sample collection, tissue collection, processing and shipment are provided in the Laboratory and Procedures Manual, respectively. Any leftover blood or tumor tissue may be stored for future research if the subject signs the optional FBR consent.

22 Blood for genetics sample will be collected to explore host genetics and to identify genetic predictors which may have a role in therapeutic response to pembrolizumab.

23 The discontinuation visit should be scheduled at the time of permanent discontinuation of all treatments (pembrolizumab, trametinib, and/or dabrafenib). The window for this visit is +10 days. Required assessments for this visit are identified in the study flow chart; additional assessments that are not flagged as required may be performed if clinically indicated (e.g., coagulation tests, thyroid function tests, etc.).

24 Perform a full physical examination on the first day of each cycle and a directed physical examination on Day 22 of each cycle. Example: full physical exam on C3D1, directed physical exam on C3D22, full physical exam on C4D1, directed physical exam on C4D22, etc.

25 Day 1 and 22 of Cycle 3: CBC with Differential, Comprehensive Chemistry Panel, Urinalysis
Day 1 ONLY from C4D1 onwards: CBC with Differential, Comprehensive Chemistry Panel, Urinalysis
Day 1 ONLY of every cycle (e.g., C3D1, C4D1, C5D1, etc.): ECOG Performance Status
Day 1 and 22 of every cycle (e.g., C3D1, C3D22, C4D1, C4D22, etc.): Dispensation of Drug Kit
Day 1 ONLY of every cycle (e.g., C3D1, C4D1, C5D1, etc.) until 18 months, then Day 1 ONLY of every other cycle: Tumor Imaging
Day 1 ONLY of every alternate cycle, as indicated (e.g., C3D1, C5D1, C7D1, etc.): ECG, ECHO, Pharmacokinetics of pembrolizumab and/or trametinib and/or dabrafenib, Anti-pembrolizumab Antibodies testing

26 pembrolizumab treated subjects in the Treatment Phase – Additional optional biopsy at disease progression is highly desired when feasible. Detailed instructions for tissue collection, processing and shipment are provided in the Procedures Manual.

27 Dermatological examination will be part of full physical examination on the first day of each cycle.

28 Updated survival status may be requested by the Sponsor at any time during the course of the study. Upon Sponsor notification, all participants who do not/will not have a scheduled study visit or study contact during the Sponsor defined time period will be contacted for their survival status (excluding participants who have a death event previously recorded).

